^f Enhanced PK sampling, as described above, is required at the time of step-up to the maximum planned dose (eg, day 3 cohort 2, day 5 cohort 3, day 7 cohort 4, etc). Additional information regarding Cycle 1 PK sampling can be found in Table 3.

Approved

Table 14. Schedule of Assessments: Schedule B (Cycle 2 and Higher)

Cycle Day	Treatment Period														EoT	EoS											
	1																										
	Relative to start of infusion																										
Hours*	Pre-dose	0	1	2	3	4	6	8	12	16	20				Pre	6		Pre	1	6							
GENERAL AND SAFETY ASSESSMENTS																											
Hospitalization ^a															X			X			X						
Concomitant Medications	→																										
Serious adverse events	→																										
Adverse events	→																										
Disease-related events	→																										
Clinical Evaluation ^c	X													X		X	X		X		X			X		X	
Vital signs, pulse oximetry ^d	X		X	X	X	X	X	X	X	X	X	X	X	X	X	X	X	X	X	X	X	X	X	X	X	X	
ECG triplicate measurement ^e	X		X ^e												X				X						X		
LABORATORY ASSESSMENTS																											
Serum pregnancy test ^f	X																										
Coagulation	X						X							X	X	X			X						X	X	
Hematology, Chemistry	X						X							X	X	X			X							X	X
Urinalysis	X													X					X							X	X
INVESTIGATIONAL PRODUCT DOSING																											
AMG 673 short term IV Infusion		X												X					X								
PK ASSESSMENTS																											
AMG 673 PK Collection ⁱ	X ^j		X ^j			X ^j	X ^j							X ^j	X ^j	X ^j					X	X	X			X	X
DISEASE and BIOMARKER ASSESSMENTS																											
Bone marrow assessments																									X ^k	X	

Footnotes defined on next page of the table

Approved

EOS = End of Study; EOT = End of Treatment; SCR = Screening

* Assessments should be taken at the time specified (in hours) from the start of infusion on that day. If a time is not specified, all assessments and collections should be pre-dose.

^a Subject must be hospitalized for a minimum of 48 hours following each dose

^b After Cycle 2, a treatment free interval may be added per the guidance in [Section 6.2.1.1.2](#).

^c Clinical evaluations will include physical exam, ECOG, and weight. Screening only: demographics, medical history, and height will also be obtained. Pre-dose clinical evaluation may occur up to 3 days prior to dose.

^d Vital signs / pulse oximetry will also be assessed prior to subject's discharge from hospital in order to detect possible signs and symptoms of infusion reactions.

^e ECGs are required per [section 7.3.8](#). ECG should be taken at the end of the infusion of the first dose in each cycle.

^f Serum pregnancy test will be performed for all females unless surgically sterile or > 2 years postmenopausal

^h This sample is optional. See Laboratory Manual for details on collection requirements.

ⁱ PK samples are required as shown for cycles 2, 3, 5 and 8 only in addition to EOT/EOS visits.

^j PK samples only collected during cycle 2 and not subsequent cycles. If Cycle 2 is not initiated immediately after Cycle 1, collect samples on day 14-19 relative to initiation of Cycle 1 per [Table 12](#).

^k During the same procedure, bone marrow samples will be collected for both response and biomarker assessments.

Approved

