6.2.1.1.1 Schedule A

The drug will be administered as short term IV infusions (approximately 30 minutes to 3 hours) on D1 and D5 of each treatment cycle followed by an infusion-free interval prior to the start of the following treatment cycle. Up to 2 additional infusions on D12 and D19 of a cycle may be implemented by DLRM recommendation.

The planned dose levels for the dose escalation cohorts are: 0.05 µg, 0.15 µg, 0.45 µg, 1.5 µg, 4.5 µg, 9 µg, 18 µg, 36 µg, 72 µg, 110 µg, 160 µg, 240 µg, 360 µg and higher if MTD is not reached (testing doses higher than 360 µg will be done via a substantial amendment for EU). The MTD or highest tested dose (or doses, in case of dose step) will be administered in the dose-expansion cohort.

Table 2. Schedule A Planned Dose Escalation Schematic^a

Number of Subjects	Target Dose ^b
1 ^c	0.05 µg/infusion
1 ^c	0.15 µg/infusion
3-4 ^c	0.45 µg/infusion
3-4	1.5 µg/infusion
3-4	4.5 µg/infusion
3-4	9 µg/infusion
3-4	18 µg/infusion
3-4	36 µg/infusion
3-4	72 µg/infusion
3-4	110 µg/infusion
3-4	160 µg/infusion
3-4	240 µg/infusion
3-4	360 µg/infusion

^a actual doses for a cohort will be up to DLRM recommendation

^b intermediate dose level(s) may be evaluated as necessary

^c in case of occurrence of a drug related safety or efficacy signal as listed below, the BLRM design would be triggered

The infusion-free interval will have a duration of 0 to 14 days depending on treatment response and recovery of blood counts, but may be extended to up to 5 weeks in case of prolonged marrow aplasia and aleukemic cytopenia after consultation with the sponsor. It may also be extended for up to 3 days from the planned duration if necessary for

logistical reasons. The DLRT may recommend on changes of the duration of the infusion-free interval for future cohorts after evaluation of PK data.

Depending on the treatment response, the following scenarios are possible in the first treatment cycle (shown for a 2-week cycle – infusions on D1 and D5 as an example):

- Tumor assessment on day 14: Subjects who show no detectable leukemic blasts in bone marrow and in peripheral blood will start the next cycle at day 21. Subjects who show detectable leukemic blasts in bone marrow or blood will start the next cycle at day 15.

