6.2.1.1.2 Schedule B

Schedule B will be initiated after preliminary safety data of AMG 673 in Schedule A (eg, MTD1 is estimated to be \geq 72 μ g) become available and may be conducted in parallel with Schedule A per sponsor's decision. For Schedule B, planned dose levels (dose per infusion) for the dose escalation cohorts are as follows: 72 μ g, 110 μ g, 160 μ g, 240 μ g, 360 μ g, 480 μ g and higher if MTD is not reached. The drug will be administered as short term IV infusions (approximately 30 minutes to 3 hours). The starting dose for the first

cohort on Schedule B will be 72 µg administered as short-term IV infusions daily (QD) during the 14-day cycle 1. No significant AMG 673 accumulation following QD dosing is predicted based on the preliminary PK analysis of Schedule A dosing. The doses administered for the cohorts following cohort 1 will include step-up doses administered in 2 day increments after the previous step-up dose (eg, cohort 2 will start with 72 µg for 2 days followed by 110 µg administered from day 3 to day 14; cohort 3 will start with 72 µg for 2 days followed by 110 µg from day 3 to day 4, followed by 160 µg from day 5 to day 14, etc). See [Table 3](#) below for more details.

Table 3. Schedule B - Cycle 1 Dosing

	D1 ^c	D2 ^c	D3	D4	D5	D6	D7	D8	D9	D10	D11	D12	D13	D14
Cohort 1	72 ^{ab}	72	72	72	72	72	72	72	72	72	72	72	72	72 ^b
Cohort 2	72 ^{ab}	72	110 ^{ab}	110	110	110	110	110	110	110	110	110	110	110 ^b
Cohort 3	72 ^{ab}	72	110 ^a	110	160 ^{ab}	160	160	160	160	160	160	160	160	160 ^b
Cohort 4	72 ^{ab}	72	110 ^a	110	160 ^a	160	240 ^{ab}	240	240	240	240	240	240	240 ^b
Cohort 5	72 ^{ab}	72	110 ^a	110	160 ^a	160	240 ^a	240	360 ^{ab}	360	360	360	360	360 ^b
Cohort 6	72 ^{ab}	72	110 ^a	110	160 ^a	160	240 ^a	240	360 ^a	360	480 ^{ab}	480	480	480 ^b

D = dose; Unit of dosage = µg

^a Dexamethasone 8 mg IV will be administered 1 hour prior to dose.

^b Additional PK samples will be taken at these time points as described in [Table 12-Table 14](#).

- [Table 13](#) PK sampling will be used only at the first dose of the target dose (highest dose planned) to be tested in Cycle 1 for each subject
- All subjects will undergo day 1 PK sampling as described in [Table 12](#).

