7. STUDY PROCEDURES

7.1 Schedule of Assessments

Approved

Table 6. Schedule of Assessments: Doses D1-D5 (Cycle 1)

Cycle Day	SCR	Treatment Period																												EoT	EoS			
	-14 to -1	1							2	3	4	5 ^a								6	7	8	14 ^b											
	Pre-dose	Relative to start of infusion														Pre-dose	Relative to start of infusion																	
Hours		0	1	2	3	4	6	8	12	16	20	24	48	72	0	1	2	3	4	6	8	12	16	20	24	48								
GENERAL AND SAFETY ASSESSMENTS																																		
Informed consent	X																																	
Hospitalization																																		
Concomitant Medications																																		
Serious adverse events																																		
Adverse events																																		
Disease-related events																																		
Clinical Evaluation ^c	X	X										X	X	X	X																			
Vital signs, pulse oximetry ^d	X	X	X	X	X	X	X	X	X	X	X	X	X	X	X	X	X	X	X	X	X	X	X	X	X	X	X	X	X	X	X	X	X	X
ECG triplicate measurement ^e	X	X	X ^h									X			X ^h																			X
LABORATORY ASSESSMENTS																																		
Serum pregnancy test ^f	X	X																																
Coagulation	X	X					X					X	X	X	X														X	X	X	X	X	X
Hematology, Chemistry	X	X					X					X	X	X	X														X	X	X	X	X	X
Urinalysis	X	X																														X	X	
Hepatitis Serology	X																																	
INVESTIGATIONAL PRODUCT DOSING																																		
AMG 673 short term IV Infusion			X																															
PK ASSESSMENTS																																		
AMG 673 PK Collection		X	X			X						X	X		X	X					X	X					X	X	X	X	X	X	X	
DISEASE and BIOMARKER ASSESSMENTS																																		
Bone marrow assessments	X																															X	X	

Footnotes defined on next page of the table

Approved

EOS = End of Study; EOT = End of Treatment; SCR = Screening

^a The Dose Level Review Team may recommend to change timing of D5 within a window of ± 1 day. In this case, timing of the following visits would be adjusted accordingly.

^b In case of extended infusion-free interval, patients must be monitored per institutional practices.

^c Clinical evaluations will include physical exam, ECOG, and weight. Screening only: demographics, medical history, and height will also be obtained. Pre-dose clinical evaluation may occur up to 3 days prior to dose.

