^d Vital signs / pulse oximetry will also be assessed prior to subject's discharge from hospital in order to detect possible signs and symptoms of infusion reactions.

^e ECGs are required per [section 7.3.8](#). ECG's: At screening 2 triplicates (total of 6 ECGs) should be done, at predose C1D1: 1 triplicate (total of 3 ECGs), post 1hr -end of infusion, 24 hours post dose and at EOS. Schedule for ECGs during cycle 1 also applies in case of intra-subject dose escalation, regardless of actual study cycle.

^f Serum pregnancy test will be performed for all females unless surgically sterile or > 2 years postmenopausal

^h Assessment should be taken at the end of infusion

Approved

Table 7. Schedule of Assessments: Doses D1-D5 (Cycle 2)

Cycle Day	Treatment Period																								EoT	EoS						
	1												5 ^b										6	7			8	14				
	Pre-dose	Relative to start of infusion											Pre-dose	Relative to start of infusion																		
	0	1	2	3	4	6	8	12	16	20	24	48	72	0	1	2	3	4	6	8	12	16	20	24	48							
GENERAL AND SAFETY ASSESSMENTS																																
Hospitalization																																
Concomitant Medications																																
Serious adverse events																																
Adverse events																																
Disease-related events																																
Clinical Evaluation ^c	X												X	X	X	X											X	X	X	X	X	X
Vital signs, pulse oximetry ^d	X		X	X	X	X	X	X	X	X	X	X	X	X		X	X	X	X	X	X	X	X	X	X	X	X	X	X	X	X	
ECG triplicate measurement ^e	X		X ^f									X				X ^f										X					X	
LABORATORY ASSESSMENTS																																
Coagulation	X						X					X	X	X	X												X	X	X	X	X	X
Hematology, Chemistry	X						X					X	X	X	X												X	X	X	X	X	X
Urinalysis	X													X																X	X	
Hepatitis Serology																																
INVESTIGATIONAL PRODUCT DOSING																																
AMG 673 short term IV infusion		X														X																
PK ASSESSMENTS																																
AMG 673 PK Collection	X		X				X					X	X		X					X	X					X	X	X	X	X	X	
DISEASE and BIOMARKER ASSESSMENTS																																
Bone marrow assessments																													X		X	

Approved

EOS = End of Study; EOT = End of Treatment; SCR = Screening

^a The Dose Level Review Team may recommend to change timing of D5 within a window of ±1 day. In this case, timing of the following visits would be adjusted accordingly.

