Hepatitis Serology	X																																																														
INVESTIGATIONAL PRODUCT DOSING																																																															
AMG 673 short term IV infusion		X																										X																																			
PK ASSESSMENTS																																																															
AMG 673 PK Collection		X	X			X				X	X	X	X	X	X	X	X	X	X	X	X	X	X	X	X	X*	X			X	X	X	X	X	X	X	X	X	X	X	X	X	X	X	X	X	X	X	X	X	X	X	X	X	X	X	X						
DISEASE and BIOMARKER ASSESSMENTS																																																															
Bone marrow assessments	X																																																												X	X	

EOS = End of Study; EOT = End of Treatment; SCR = Screening
 X* = at end of infusion perform corresponding assessment (ie, ECG at timepoint 1hr C3D1 with X* should be taken at end of infusion).
 NOTE: Use Table 6 in combination with Table 9 for Cycle 1, intra subject, dose step escalation, 4 dose schedule.
^a The Dose Level Review Team may recommend to change timing of D 5/12/19 within a window of ±1 day. In this case, timing of the following visits would be adjusted accordingly.
^b In case of extended infusion-free interval, patients must be monitored per institutional practices.
^c Clinical evaluations will include physical exam, ECOG, and weight. Screening only: demographics, medical history, and height will also be obtained. Pre-dose clinical evaluation may occur up to 3 days prior to dose.
^d Vital signs / pulse oximetry will also be assessed prior to subject's discharge from hospital in order to detect possible signs and symptoms of infusion reactions.
^e ECGs are required per section 7.3.8. ECG's: at predose, post 1hr -end of infusion, 24 hours post dose and at EOS.
^f Serum pregnancy test will be performed for all females unless surgically sterile or > 2 years postmenopausal

Approved

Table 10. Schedule of Assessments: Doses D1/D5/D12/D19 (Cycle 2)

Cycle Day	Treatment Period																												12 ^a	19 ^a	28 ^b	EoT	EoS																										
	1							5 ^b							6			7			8																																						
	Pre-dose	Relative to start of infusion														Pre-dose	Relative to start of infusion																	Pre-dose	Relative to start of infusion			Pre-dose			Relative to start of infusion																		
	0	1	2	3	4	6	8	12	16	20	24	48	72	0	1	2	3	4	6	8	12	16	20	24	48		0	1	4		0	1	4																										

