DISEASE and BIOMARKER ASSESSMENTS																																											
Bone marrow assessments	X																																								X ^k		X

Footnotes defined on next page of the table

Approved

EOS = End of Study; EOT = End of Treatment; SCR = Screening

- ^a Assessments should be taken at the time specified (in hours) from the start of infusion on that day. If a time is not specified, all assessments and collections should be pre-dose.
- ^b The following assessments should be performed relative to the day 14 dose. Cycle 2 should begin immediately after Cycle 1 with no treatment free interval (see [Section 6.2.1.1.2](#)). The samples in dark gray are only collected if the subject will not initiate cycle 2 immediately after cycle 1. If cycle 2 is initiated immediately after cycle 1, then collect per [Table 14](#) (refer to footnote J).
- ^c Clinical evaluations will include physical exam, ECOG, and weight. Screening only: demographics, medical history, and height will also be obtained. Pre-dose clinical evaluation may occur up to 3 days prior to dose.
- ^d Vital signs / pulse oximetry must be collected as described above but may be collected at site more frequently per institutional policy or by recommendation of PI. Additional assessments do not need to be reported to EDC unless related to an adverse event but must be kept in source. Subjects will also be assessed prior to discharge from hospital in order to detect possible signs and symptoms of infusion reactions.
- ^e ECGs are required per [section 7.3.8](#). ECG's: At screening 2 triplicates (total of 6 ECGs) should be done, at predose C1D1: 1 triplicate (total of 3 ECGs), post 1hr -end of infusion, 24 hours post dose and at EOS. Schedule for ECGs during cycle 1 also applies in case of intra-subject dose escalation, regardless of actual study cycle.
- ^f Serum pregnancy test will be performed for all females unless surgically sterile or > 2 years postmenopausal
- ^g Refer to [Table 3](#) for planned dosing regimen

ⁱ This sample is optional. See Laboratory Manual for details on collection requirements.

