### **9.7.1 Analyses of Pharmacokinetic or Pharmacokinetic/Pharmacodynamic Endpoints**

Serum concentrations of AMG 673 will be determined using a validated assay. PK parameters will include, but are not limited to half-life ( $t_{1/2}$ ; if feasible), maximum observed concentration ( $C_{\text{max}}$ ), minimum observed concentration ( $C_{\text{min}}$ ), area under the concentration-time curve from time 0 to the time of the last quantifiable concentration ( $\text{AUC}_{0\text{-last}}$ ) and clearance. Pharmacokinetic parameters will be estimated using standard non-compartmental approaches and summarized by dose level using means, standard deviations, medians, minimums, and maximums.

Serum concentrations below the lower limit of quantifications will be set to zero for the estimation of the pharmacokinetic parameters for each subject and for the calculation of the summary statistic for each time point. Actual dosing and sampling time will be used for all calculations. The reasons for excluding any sample from the analyses will be provided.

Individual concentration-time data will be summarized by dose level. Individual concentration-time data will also be tabulated and presented graphically. Summary statistics will be computed for each sampling time and parameter as appropriate.

Additional PK analyses, including but not limited to analysis of the relationship between AMG 673 dose and exposure parameters (AUC and  $C_{max}$ ) and dose proportionality assessments, may also be conducted. Based on the review of the data, analyses to describe the relationship between AMG 673 exposure and either pharmacodynamic effect and/or clinical outcome may also be performed.

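### The first post-dose PK sample on D1/D5 and in Schedule B is timed 1 hour from infusion start, not at end of infusion, so observed Cmax may be understated by an amount that varies with infusion length

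*Protocol*

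**What the plan says.** **Timing.** The hour columns of the Schedule A tables (Protocol 7.1, Tables 6-11) run "Relative to start of infusion". For Schedule B, notes to Tables 12 and 14 read "Assessments should be taken at the time specified (in hours) from the start of infusion on that day", and Table 13 counts hours from the start of the stepped-up infusion.

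**Infusion length.** Protocol 6.2.1.1.1: "The drug will be administered as short term IV infusions (approximately 30 minutes to 3 hours) on D1 and D5 of each treatment cycle". Section 6.2.1.1.2 gives the same range for Schedule B.

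**PK marks.** Tables 7, 12 and 14 read cleanly: the first post-dose PK mark on day 1 is a plain X at 1 hour. Some columns of the other tables are displaced in the text available, but no end-of-infusion flag is visible on the D1/D5 PK marks in Tables 6 and 8-11, or in Table 13.

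**Where end of infusion is specified.** The ECG in the same column of Tables 6-8 carries a footnote: "Assessment should be taken at the end of infusion". In Tables 9-11, X* means "at end of infusion perform corresponding assessment", and it appears on PK marks at the later doses, most clearly in Tables 10 and 11.

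**Use of Cmax.** It is a named secondary PK parameter (Protocol 10.1.1; SAP 2.1). SAP Section 5 defines it as the maximum observed serum concentration. SAP 9.7.1 summarises PK parameters by dose level from non-compartmental methods and adds that "dose proportionality assessments, may also be conducted".

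**The concern.** With constant-rate infusion, concentration peaks when the infusion stops. A sample fixed at 1 hour from the start coincides with that moment only for an infusion of about 1 hour. For a 2-3 hour infusion it is drawn while drug is still running in. For a 30-minute infusion it comes half an hour after the peak.

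Observed Cmax then mixes the true peak with the gap between end of infusion and the nearest sample. Two subjects on the same dose with different infusion lengths could differ in recorded Cmax partly because of sampling. Cmax is summarised by dose level, may be used for dose proportionality and exposure-response work, and is among the PK information open to the Dose Level Review Team. SAP 9.7.1 uses actual dosing and sampling times; that corrects the time axis for AUC but cannot supply a concentration that was not measured.

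The protocol already ties the ECG and some later-dose PK marks to end of infusion. Its history suggests how the gap arose: the Amendment 2 rationale records that infusions were lengthened from a maximum of 1 hour to 3 hours.

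**Working it through.** The plan states no figure to reproduce. The question is how far observed Cmax can fall below the end-of-infusion (EOI) level.

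**Inputs from the documents**
- Infusion length T: 0.5 to 3 h (Protocol 6.2.1.1.1, 6.2.1.1.2).
- Day 1 samples: 1, 4 and 6 h in Tables 12-14 (Table 13 after allowing for displaced columns); about 1 and 4 h in Table 6 on the same allowance; 1 and 6 h in Table 7 as it reads.
- Half-life: 21 days anticipated in humans (2.2); 167-178 h in monkeys, with biphasic decline (2.2.2).
- Section 6.2.1.1.2 predicts no significant accumulation on daily dosing, from preliminary human data.

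**Assumptions.** The documents give no human distribution constants. I took mono-exponential half-lives of 21 days, 170 h, 9.28 h and 6 h, and bi-exponential decline with an 80% fast share, fast half-life 1-12 h and slow half-life 170 h.

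**Are the shorter half-lives plausible?** Under mono-exponential decline, accumulation over 14 daily doses is:
- 21 days: (1 − 2^(−14/21)) / (1 − 2^(−1/21)) = 0.370/0.0325 ≈ 11-fold.
- 170 h: (1 − 2^(−336/170)) / (1 − 2^(−24/170)) = 0.746/0.0932 ≈ 8-fold.

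Neither fits a prediction of little accumulation. If little means a steady-state ratio of 1.2 (my assumption), 1/(1 − 2^(−24/h)) = 1.2 gives h ≈ 9.3 h.

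**Formulas.** For rate constant k = ln 2 / half-life, concentration is proportional to (1 − e^(−kt))/(kT) during infusion and falls as e^(−k(t−T)) afterwards. The bi-exponential case is the weighted sum of two such terms.

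**The 1-hour sample alone**, as a share of the EOI level: 33-48% for a 3 h infusion, 50-61% for 2 h, 100% for 1 h, 77-100% for 0.5 h. With elimination ignored it is simply 1/T for T of 1 h or more.

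**Observed Cmax**, the highest of all samples, as a share of the EOI level. Example: half-life 6 h, T = 3 h, sample at 4 h gives 2^(−1/6) = 0.89; T = 2 h gives 2^(−2/6) = 0.79.

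| Assumed decline | 0.5 h | 2 h, samples 1/4/6/24 h | 3 h, samples 1/4/6/24 h | 2 h, samples 1/6/24 h | 3 h, samples 1/6/24 h |
|---|---|---|---|---|---|
| Mono, 21 days | 100% | 100% | 100% | 99% | 100% |
| Mono, 170 h | 100% | 99% | 100% | 98% | 99% |
| Mono, 9.28 h | 96% | 86% | 93% | 74% | 80% |
| Mono, 6 h | 94% | 79% | 89% | 63% | 71% |
| Bi, fast 12 h | 98% | 91% | 95% | 83% | 87% |
| Bi, fast 6 h | 95% | 84% | 91% | 71% | 77% |
| Bi, fast 2 h | 87% | 63% | 79% | 56% | 53% |
| Bi, fast 1 h | 77% | 61% | 68% | 61% | 48% |

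A 1 h infusion gives 100% throughout. With the 4 h sample, a 2 h infusion loses more than a 3 h one, because that sample comes 2 h after its end and not 1 h. The error is therefore not even monotone in infusion length.

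**With the first sample at EOI** the ratio is 100% for every T, apart from the ±15 minute window in Section 7.2. At a 6 h half-life that window costs 1 − 2^(−0.25/6) ≈ 3%, and more if there is a fast distribution phase.

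**The case against.** A reader might infer that the peak is never sampled, or that recorded Cmax after a 3-hour infusion is one third of the truth. The documents support neither. The one-third figure describes the 1-hour sample. Cmax is the highest of all samples, and a 4-hour or 6-hour sample follows the end of every permitted infusion. If elimination is ignored, which is what yields one third, that later sample equals the EOI level and the loss is zero. At the 21-day half-life the protocol anticipates, and near the monkey value, the loss is negligible. This stands, and it limits the point to possible understatement.

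Other objections also carry weight:
- Several tables are damaged in the text available, so a missing flag is weaker evidence there. Tables 7, 12 and 14 are clear enough to carry the point.
- The ECG contrast does not extend to Table 13, whose ECG footnote does not mention end of infusion.
- Section 7.2 sets a PK window that refers to end of infusion, and Section 7.3.12 leaves collection details to a laboratory manual not seen here. The manual may hold the missing instruction, but the protocol tables would then need to agree with it.
- ECG footnotes pair 1 hour with end of infusion, which suggests a nominal 1-hour infusion, for which there is no error. How often infusions run longer is unknown.
- Dose-proportionality and exposure-response analyses are optional, and dose decisions rest chiefly on DLTs, the Bayesian model and team review. No planned comparison of D1/D5 with D12/D19 Cmax was found.

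**Conclusion.** The point holds as a gap in the sampling schedule. Followed as written, the D1/D5 and Schedule B tables give a first post-dose PK sample that misses end of infusion unless the infusion lasts about 1 hour, and observed Cmax can then depend on infusion length through sampling alone.

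The size depends on kinetics the documents do not give. The loss is nil to about 2% for half-lives of 170 h to 21 days. Under the assumed faster decline it is about 5-40% for 2-3 h infusions, and up to about 50% if only 1 h and 6 h samples exist. A 30-minute infusion could lose up to about 23%. Faster decline is not established, but the little-accumulation prediction in Section 6.2.1.1.2 is hard to square with the longer half-lives under simple mono-exponential decline.

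This is an inexpensive improvement to a secondary PK parameter. It does not undermine the primary safety analysis or the dose-escalation rule.

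**What to change.** 1. Extend the existing end-of-infusion flag (footnote or X*) to the 1-hour PK sample on D1/D5 in Tables 6-11 and to the corresponding sample in Tables 12-14. Draw it under the line rules of Section 7.3.12.
2. Align the laboratory manual with the tables.
3. Keep Cmax as the maximum observed concentration, as SAP Section 5 defines it. It might seem natural to take Cmax only from the end-of-infusion sample, but that would override the definition whenever another sample is higher.
4. In SAP 9.7.1, present Cmax with actual infusion duration. Section 6.2.1.1.3 already requires infusion start and stop times on the eCRF, so no new data are needed.

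The cost is a footnote change and a matching manual update, with no added blood draw. The drawback is a mixed data set: subjects already sampled at 1 hour must be labelled as such in the Cmax summary.
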